### 5.2 Secondary Analyses of Primary Objective 1 Outcome Measure

#### 5.2.1 Adjustment for Covariates

A secondary analysis of the primary Objective 1 outcome measure will adjust for additional covariates that are associated with the primary outcome. This secondary analysis will be the same as the primary analysis (i.e., it will still adjust for the baseline value of the outcome and include HCS-specific random intercepts), except that it will include additional covariates. The primary goal of this secondary analysis is as a sensitivity analysis, in which we will investigate the degree to which the treatment effect estimate ( $\beta$ ) from the primary analysis changes after covariate adjustment; thus, we plan focus on the magnitude of the change in the estimate rather than conduct inference on the treatment effect estimated under this secondary analysis.

The following approach will be utilized to identify the covariates for potential inclusion in the secondary analytic model of the primary outcome measure. First, we will consider a candidate set of clinic-level covariates (described below). Because of our small sample size ( $n=12$ ) for the clinic-level primary outcome, we are limited in the number of covariates we can include in the outcome model to avoid overfitting, which can lead to unstable coefficient estimates. Consequently, we plan to conduct baseline analyses (detailed below) to identify a subset of these predictors to adjust for. The goal of these baseline analyses is to identify which covariates are associated with the clinic-level number of patient years of OUD treatment during a 1-year period pre-randomization, after adjusting for this measure in prior baseline years (to mimic the primary analysis but using only baseline data). The planned baseline analyses will proceed as follows.

- 1) Consider the pre-randomization data from the two years prior to randomization (Period 1 = two years prior to randomization; Period 2 = year prior to randomization). Denote B1 as the “baseline” value of the outcome measure in Period 1 and B2 as the “baseline” value in Period 2. Obtain values of each of the clinic-level covariates being considered during the earlier baseline period (Period 1), such as the proportion of patients seen in the clinic during Period 1 who were female.
- 2) Conduct a regularized (lasso) regression of the B2 values on the B1 values as well as all of the candidate clinic-level covariates for Period 1 (earlier baseline period). Lasso regression avoids overfitting by penalizing the magnitude of the coefficients such that some of the coefficients may be shrunk to exactly zero. The B1 value of the outcome will be “forced” into the model (i.e., the corresponding coefficient will not be penalized). We will use cross-validation initially to select the best-fitting value of the tuning parameter  $\lambda$  (which controls the number of non-zero coefficients). Specifically, we will perform a “leave-one-cluster-out” cross-validation as follows. For each candidate value of the tuning parameter  $\lambda$ , we predict the B2 values of each HCS using a regularized mixed-effect model fitted with the data from all other HCSs. We then compute the mean squared error (MSE) of the prediction, and take the average of these MSEs across all HCSs (“the cross-validated MSE”), as the measure of the performance of the candidate value of the tuning parameter  $\lambda$ . We select the candidate value of the tuning parameter  $\lambda$  with the smallest cross-validated MSE.
- 3) If the selected value of the tuning parameter  $\lambda$  is such that there are more than 2 non-zero coefficients, we plan to vary the value of  $\lambda$  such that no more than 2 covariates have non-zero coefficients. These 2 covariates will be the ones that we include in the covariate-adjusted analysis (except that the time window for the covariates included in the outcome model will be over the full 2-year baseline period, rather than just over Period 1).

With 12 clinics and 4 variables (intervention indicator, baseline value of the outcome, plus 2 covariates), this proposed covariate-adjusted analysis would have 3 observations (clinics) per variable. Although there is no firm rule on the maximal number of variables able to be included in the model, recent literature has suggested that having as few as two subjects per variable in a standard linear regression model did not adversely impact parameter estimation.

Candidate set of covariates: We identified a broad set of covariates based on known and hypothesized predictors of initiation in and retention to medication treatment for OUDs from the literature and discussions with study co-investigators. Each covariate will be defined at a patient level, and then aggregated into Period-specific (i.e., Period 1 and Period 2) clinic-level measures (e.g., mean age of patients seen in a clinic in Period 1 or 2, proportion of patients with  $\geq 1$  depression diagnosis) to be considered for the covariate-adjusted analysis of the clinic-level outcome.

- 1) Age
  - a. Continuous: mean age
  - b. Categorical: proportion in each group (<25, 25-44, 45-64, ≥65)
  - c. Binary: proportion <45
- 2) Gender: proportion female
- 3) Race/ethnicity: proportion in each of the following groups:
  - a. Hispanic
  - b. Non-Hispanic Asian
  - c. Non-Hispanic Black or African American,
  - d. Non-Hispanic White,
  - e. Non-Hispanic Other race (any of the following, as well as each of the following groups separately):
    - i. American Indian / Alaska Native
    - ii. Native Hawaiian or Pacific Islander
    - iii. Multiple race
    - iv. Other race
  - f. Missing/Unknown
- 4) Number of days with an OUD diagnosis: proportion of patients with 0, ≥1, ≥2, ≥5, ≥10
- 5) Number of days with a diagnosis of each of the following conditions (using clinic-level proportions as for OUD above):
  - a. Depression
  - b. Anxiety
  - c. PTSD
  - d. ADHD
  - e. Other mental health conditions
  - f. Any mental health condition (a-e above)
  - g. Alcohol use disorder
  - h. Cannabis use disorder
  - i. Stimulant use disorder
  - j. Other (non-opioid) substance use disorder
  - k. Any substance use disorder (g-j above)
    - i. Also including OUD
    - ii. Excluding OUD
  - l. HCV
- 6) Number of days with an ICD code for housing instability / homelessness (using clinic-level proportions as for OUD above)
- 7) Neighborhood-level SES measures, deciles across patients of:
  - a. median household income
  - b. percent below the federal poverty line
  - c. percent unemployed
- 8) Buprenorphine prescribers
  - a. number in the clinic
  - b. as a percentage of all prescribers in the PC clinic
- 9) Rurality of residence (rural urban commuting codes of zip code): proportion in each group (urban, large rural city/town, small and isolated small rural town)
- 10) Quadratic term of baseline outcome

Covariates will be centered and standardized to have mean 0 and standard deviation (SD) of 1 so that they have the same scale. We note that many of the above measures are expected to be highly correlated; however, the proposed lasso approach is able to select from among correlated measures, based on the predictive ability.

## **5.2.2 Modified Analyses Accounting for Success of Implementation**

Our Objective 1 analysis considers days of OUD treatment over the entire follow-up period since randomization. However, it took time for HCSs to hire the NCM, and for the NCM to start seeing patients once hired, and it is possible some may have never succeeded in implementing the model. We therefore plan to conduct two modified analyses, which will apply the same statistical model as the primary analysis but will either modify the definition of the follow-up period over which the Objective 1 outcome measure will be calculated or will restrict which HCSs are included.

### **5.2.2.a. Analysis During the Period in Which the NCM was Seeing Patients**

First, we will modify the time period over which the main outcome is calculated to only include periods after which the NCM has engaged a patient in OUD treatment in the intervention clinic. For example, if the intervention clinic of a HCS hired the NCM 16 weeks after randomization and s/he was trained 8 weeks later and s/he engaged the first patient 1 week after training, for that HCS we would define the time period from 23 weeks post randomization until the end of the follow-up period, for both the clinic randomized to the PROUD intervention and the clinic randomized to UPC.

### **5.2.2.b. Analysis Limited to Clinics that Successfully Implemented the MA Model**

Second, we will further restrict the set of clinics analyzed by excluding HCS from the analysis if the clinic randomized to the intervention in that HCS did not successfully implement the MA model. Successful implementation is defined as the NCM at the intervention clinic at that HCS seeing at least 30 patients. The choice of 30 patients was selected *a posteriori* as a level that several HCS had achieved and which was hypothesized as a tipping point for the clinic to be known as providing OUD treatment within the HCS. If more than 2 HCS are excluded, then we may not be able to fit the mixed-effect model; if that is the case then we will instead describe the outcome across intervention arms in these sets of clinics.

## **5.2.3 Sensitivity Analysis Addressing the Algorithm for Assigning Patients to Clinics**

The primary algorithm for clinic assignment (see Section 3) prioritizes the clinic that the patient visited pre-randomization. If a patient visits the UPC clinic pre-randomization but then starts going to the PROUD clinic to receive care from the NCM, under this approach for clinic assignment any medication days of treatment will be “counted” toward the UPC clinic, which could bias the effect of PROUD toward the null. To address this issue, we plan to describe the number of patients with OUD (diagnosed any time during the study period) treated in the intervention clinic during follow-up who were assigned to the UPC clinic (see Section 3 above). If we observe that ever occurs at a health system, we will apply an alternate algorithm as a sensitivity analysis, in which we will assign patients to clinics based on the number of visits to the clinic during the post-randomization period.

## **5.2.4 Sensitivity Analyses Focused on Assumptions Made in Estimating Patient-Years of OUD Medication Treatment (Objective 1: Main Implementation Outcome)**

While medication dispensings are only a proxy for ingestion of medications, they are the gold standard for ascertaining medication use with EHR and claims data. When evaluating patient days of OUD treatment, only medication orders are available at most PROUD health systems.

Pharmacy dispensings are complete at only one health system. Medication orders suffer from the same limitation of no assurance the medication was ingested plus medication orders could have been written and never dispensed. We expect that this is uncommon as preliminary data from Phase I at the health system with complete dispensings indicated 98% of patients with a buprenorphine order have a dispensing within 60 days of the order). However, medication dispensing data includes dispensed refills, but orders only include an indication that there can be a refill. Preliminary data from Phase I at this health system indicate approximately 14% of buprenorphine orders contain at least 1 refill on the order.

To address limitations of medication orders, we plan to conduct sensitivity analyses where we replicate the objective 1 main outcome analysis using different assumptions for calculating days of OUD medication treatment to see if there are changes in results and conclusion. Specifically, the sensitivity analyses below include more restrictive objective 1 outcome analyses with fewer assumptions about medication use and refills. In addition, we propose sensitivity analyses to address assumptions made in smoothing gaps between medication orders and/or procedures, a sensitivity analysis to add methadone maintenance therapy from the 1-2 health systems that have such data, and an analysis using dispensing data where available for at least some patients in both trial clinics within a health system.

#### **5.2.4.a. Omitting Last Order in an Oral Buprenorphine Treatment Episode**

To address the potential limitations of medication orders, we will conduct sensitivity analyses with the objective 1 main outcome restricted to episodes of treatment with at least two oral buprenorphine orders if the patient has only oral buprenorphine orders (majority of patients), with the last order in the episode omitted in case it was not picked up and taken by the patient. This sensitivity analysis also addresses any short-term buprenorphine therapy to assist with opioid tapers. This does not impact oral buprenorphine captured by procedure codes when given in the office or any injectable buprenorphine, buprenorphine implants, or injectable XR naltrexone. We will also describe the number of treatment days that are excluded in this restrictive analysis by intervention arm and health system. When the last order is omitted, all refills after the last order are also omitted.

#### **5.2.4.b. Vary the Allowable 7-day Gap to Define Continuous Use Episodes**

To address the limitation that we smooth small gaps of  $\leq 7$  day between medication orders and/or procedures to arrive at continuous episodes of OUD medication use, we will vary the allowable  $\leq 7$  day gap to smaller and larger values (e.g., 2 days, 5 days, 10 days based on descriptive data) when estimating the objective 1 main outcome in this sensitivity analysis. For example, the main analysis treats a 10 day order for buprenorphine on 1/1/2019 and a 10 day order for buprenorphine on 1/15/2019 as one continuous episode lasting from 1/1/2019 to 1/24/2019 (24 days) because the gap between when the first order ran out and the second order began is  $< 7$  days. Altering the allowable gap to only 2 days would result in two different episodes (1/1/2019 – 1/10/2019 and 1/15/2019–1/24/2019) that contribute 20 days of treatment.

#### **5.2.4.c. Incorporating Dispensings Data to Define Days of OUD Treatment**

For the health systems with outpatient pharmacies in both intervention and usual care clinics (including one health system that has complete dispensing data), we will estimate days of OUD treatment in this sensitivity analysis using a combination of medication orders and dispensing data. For each dispensing, if its dispense date (rxdate) is in “the range” of an order date or a refill date, then it is considered to be linked to that order or refill and dropped in calculations; otherwise, this dispensing is considered as not linked to any order and added to the calculation of days covered. The range is defined as dispensed within 30 days after the order/refill’s start date (an

order's start date is the order's date; a refill's start date is derived from the original order's date and days supply).

To characterize the potential for incomplete ascertainment of OUD medication treatment, we will describe 1) what proportion of patients have a buprenorphine order but not a dispensing for buprenorphine within 30 days of the order and 2) what proportion have a dispensing for buprenorphine but do not have a buprenorphine order 30 days prior to the dispensing. We will vary the 30-day window between order and dispensing (e.g., 60 days), and report by period (e.g., baseline and post-randomization) and by trial arm.

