10.3.4 Use of EHR Orders for Buprenorphine and Injectable Naltrexone

Most sites in the PROUD trial do not provide us with data on dispensed medications but instead provide EHR prescription orders. Orders could have been written and never dispensed. However, we expect that is uncommon for buprenorphine. We will address this limitation by conducting sensitivity analyses with the outcome restricted to episodes of OUD treatment with at least a series of two orders (suggesting that the patient picked up and used the first prescription). We will also use data from the two sites that are health plans, which can therefore provide dispensed medications (KPWA and HF), to conduct sensitivity analyses to see if use of dispensed medications (compared to medication orders) changes main results at those two sites.

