## 8.0 OTHER CONSIDERATIONS

### 8.1 Missing Data

Given that the primary and secondary outcomes rely on the EHR data or insurance claims data, if there is no evidence of a particular event, such as provision of buprenorphine or a visit to the ED, we will assume that the event did not occur. These same assumptions apply to the only covariate in the primary analyses of the primary Objective 1 and Objective 2 measures (baseline value of the respective measure in the 2 years prior to randomization).

Our primary Objective 1 outcome uses medication orders to capture days of OUD medication treatment as orders were available for all health systems and dispensings are considered incomplete at 5 of the 6 health systems. However, because dispensing data and not medication orders are considered the gold standard, we will conduct sensitivity analyses in which we estimate the primary outcome at each health system using only medication dispensing data in the 3 health systems that have some dispensing data and pharmacies in both the usual care and intervention clinics (Section 5.2.4).

For Objective 2, given our visit-based sample we are not able to identify when a patient is no longer observable. To address this, we will conduct a sensitivity analysis for our Objective 2 outcome among the two health systems that are health insurance plans in which we use enrolled samples (Section 5.4.3). We will also conduct sensitivity analyses that restrict to patients with evidence of being active in the health system post-randomization (as described above in Section 5.4.2).

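### SAP 5.2.4.c only adds dispensings to orders, so it cannot detect days inflated by unfilled orders or refills; the dispensing-only analysis promised in 8.1 is not specified.

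*SAP*

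**What the plan says.** SAP 4.1.1 and Appendix A build the primary outcome from orders and procedures. For an oral order, the supply is multiplied by the number of refills plus one.

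SAP 5.2.4 names two weaknesses of orders: "medication orders could have been written and never dispensed", and "orders only include an indication that there can be a refill". It gives two Phase I figures from the one system with complete dispensings: "98% of patients with a buprenorphine order have a dispensing within 60 days of the order", and "approximately 14% of buprenorphine orders contain at least 1 refill on the order". It says that the sensitivity analyses include "more restrictive objective 1 outcome analyses with fewer assumptions about medication use and refills", and lists the dispensing analysis as an addition to these.

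Section 5.2.4.c combines orders with dispensings. A dispensing within 30 days after the start of an order or refill counts as linked and is left out; "otherwise, this dispensing is considered as not linked to any order and added to the calculation of days covered". Appendix A repeats this rule, the shell for Supplementary Table 5 carries the combined version, and 5.2.4.e reuses it. A second paragraph of 5.2.4.c describes, by period and arm, the share of patients who have an order but no dispensing within the window.

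Section 8.1 refers back to 5.2.4 but says the outcome will be estimated "using only medication dispensing data in the 3 health systems" that have some such data. Protocol 10.3.4 plans to use dispensing data from two health plans "to see if use of dispensed medications (compared to medication orders) changes main results at those two sites".

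**The concern.** Both weaknesses named in 5.2.4 push the day count up. A check on them must be able to take days away when the pharmacy record shows no fill. The rule in 5.2.4.c has no such step: dispensing data enter only where they supply days that the orders did not.

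If prescribers in one arm wrote more refillable orders, or more orders that were never collected, the order-based difference between arms would be distorted. The re-estimated outcome in 5.2.4.c would carry the same distortion.

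There is also a pre-specification problem. Sections 5.2.4.c and 8.1 describe two different calculations under one cross-reference, and the protocol describes a third scope. An analyst cannot satisfy all of them with one analysis, and would have to choose after the data are in.

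**Working it through.** **Reproducing the SAP's own counts.** The day-count rule is: take the union of covered days; smooth gaps of 7 days or less; allow 14 days from buprenorphine to naltrexone; and set supply = days per fill × (refills + 1).
- Section 5.2.4.b: two 10-day orders on 1/1 and 1/15/2019 give 24 days with the 7-day gap and 20 with a 2-day gap, as stated.
- Section 4.1.1: quantity 60, 2 per day, 2 refills gives 60/2 × 3 = 90 days, as stated.

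**Three measures on the same records** (treatment days; linkage window 30 days as in 5.2.4.c):

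| Record | Primary (orders) | 5.2.4.c (orders + unlinked dispensings) | Dispensings only (8.1) |
|---|---|---|---|
| 30-day order, 2 refills, nothing dispensed | 90 | 90 | 0 |
| Same order, first fill only dispensed | 90 | 90 | 30 |
| 30-day order, 7 days dispensed | 30 | 30 | 7 |
| 30-day order undispensed, plus an unlinked 30-day dispensing | 30 | 60 | 30 |

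The second column never drops below the first, because it is the union of the order days with something else. In 50,000 simulated buprenorphine-only patients (assumed fill rates of 30% to 98%, plus random unlinked dispensings), 5.2.4.c fell below the primary count in 0 and above it in 32,965. The dispensing-only count fell below the primary in 39,921. The last two counts depend on the assumed inputs; the zero follows from the rule.

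**One technical exception.** Take a 30-day buprenorphine order on day 1 and a 28-day naltrexone injection on day 41. The 10-day gap is bridged by the 14-day rule, giving 30 + 10 + 28 = 68 days. An unlinked 7-day buprenorphine dispensing on day 41 switches that rule off, because the first day after the gap is no longer naltrexone alone. The count becomes 30 + 28 = 58. This is an artefact of smoothing and removes no unfilled order.

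**How many order-days could come from refills.** The documents give the share of orders with at least one refill (14%) but not the number of refills. Let each such order carry r refills, with equal supply per fill (both assumed).

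Share = 0.14r / (1 + 0.14r)
- r = 1: 0.14/1.14 = 12.3%
- r = 2: 0.28/1.28 = 21.9%
- r = 5: 0.70/1.70 = 41.2%

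These are shares before overlap with later orders is removed.

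**Scope side by side.** Section 5.2.4.c: orders plus dispensings, at systems with pharmacies in both clinics. Section 8.1: dispensings only, 3 systems. Protocol 10.3.4: dispensed versus ordered, 2 sites. Section 5.2.4: dispensings complete at one system only.

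**The case against.** Several points on the other side have weight.

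- **Restriction is the job of 5.2.4.a.** That analysis requires at least two oral orders, drops the last order and its refills, and reports the excluded days by arm and system. This is a partial answer. It uses no dispensing data, applies to patients with only oral buprenorphine orders, and leaves earlier unfilled orders and refills in.
- **Section 5.2.4.c has a valid purpose of its own.** It looks for treatment that no order recorded. Where patients use outside pharmacies, an add-only rule is defensible, since removing unlinked orders would turn missing data into zero treatment. This stands, and the analysis should be kept.
- **Unfilled orders are described by arm and period.** This also stands. So a reader who infers that nothing based on dispensings could reveal an arm imbalance goes too far. But the description counts patients, does not address refills, and does not re-estimate the outcome.
- **The 98% figure suggests that few patients never fill at all.** It does bear on that, but it is patient-level, comes from one system, and says nothing about whether refills were filled.

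A reader might also infer that the 5.2.4.c result is bound to look reassuring. It is not. Days per patient rise, but the estimate is a between-arm difference adjusted for baseline. Dispensings added mainly in usual-care clinics would shrink it, and additions in the baseline period change the covariate.

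**Conclusion.** Two findings hold. First, the re-estimated outcome in 5.2.4.c, and with it Appendix A, 5.2.4.e and the table shell, cannot detect days inflated by unfilled orders or refills, which are the weaknesses 5.2.4 sets out. Second, 8.1 and Protocol 10.3.4 promise comparisons that 5.2.4 does not contain, and they disagree on the number of systems.

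The size of any over-counting cannot be derived from the documents. The 12%, 22% and 41% are shares of order-days that come from refills under assumed refill counts. To read them as bias would require every refill to go unfilled, with no overlap with later orders, and a bias in the treatment effect would further require a difference between arms. Nothing in the documents shows that the primary effect is inflated.

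The primary test is unaffected. What is weakened is the claim that the order-based result has been checked against the source the SAP itself calls the gold standard.

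**What to change.** - In 5.2.4.c and Appendix A, specify a dispensing-based count at the one system with complete dispensings. Compute days from dispensings plus procedures and injectables, so that an oral order or refill with no dispensing contributes zero days.
- Report it beside the orders-only result for both clinics and for the baseline period. With one intervention and one usual-care clinic it is descriptive; the 12-clinic mixed model cannot be fitted to it.
- Keep the add-only measure as a separate analysis, labelled as a check for missed treatment, where dispensings are partial. Do not apply dispensing-only counting to systems with incomplete dispensings.
- Align 5.2.4.c, 5.2.4.e, 8.1, Appendix A and the Supplementary Table 5 shell, and state one number of systems for each analysis, noting the departure from the protocol's two sites.
- Tabulate refills per order by arm, which would replace the assumed values above.

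The cost is SAP wording and modest programming. The data are already in the collection plan.
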